**5.5 End of study**

The end of the study will be when the final participant has completed their 6-week post-transplant review. Participants will complete their final questionnaire and be asked to return their wearable device and journal. This can take place during their scheduled outpatient appointment to prevent repeated returns to hospital for the participant. Following return, devices will be passed to the research team for cleaning and returned to factory status. Participants will not be entitled to keep their wearable device.

An end of study notification will be submitted to the HRA within 90 days of the end of the study.

## 6) STUDY PARTICIPANTS

Study participants must meet all inclusion criteria. Meeting any of the exclusion criteria means that they would be unable to participate in the trial. Should any of the exclusion criteria take place after enrolment then the participant will be removed from the study.

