### 6.2 Exclusion Criteria:

[figure not shown]
- Deceased donor transplant recipient
- Patients unable to wear or tolerate the wearable device
- Unstable angina pectoralis, recent myocardial infarction, recent cerebrovascular accident, or new arrhythmia
- Patient declines or is unable to participate in the exercise programme
- Patient lacks capacity to give informed consent to participate in the trial
- Non-English language
- Patient has no access to a smart device to download the OURa/Withings Health Mate/Corsano Research Trials app

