#### 6.4 Participants who withdraw consent [or lose capacity to consent]:

Participants can withdraw consent at any time without giving any reason, as participation in the research is voluntary, without their care or legal rights being affected. There is no change to their usual management based on their participation, or withdrawal, from this study.

Participants will be asked whether any pseudonymised data collected so far, can be used as part of the analysis of the study. Data would include wearable data (biometric, activity, sleep) and paper surveys linked to their study ID only. Links between their study ID and any identifiable data would be permanently erased at the time of consent withdrawal.

Once full data collection has been completed, all data will be anonymised and no longer linked to a study ID. It would not be possible to remove individual participant data from the analysis of this trial after the point of anonymisation.

Participants will continue to be involved with data collection after discharge from hospital, therefore any loss of capacity to consent during anaesthesia and/or whilst a patient on intensive care will be resolved at discharge. For any patient that may die during their

admission, however unlikely, will also be included in analysis as this is an extremely important adverse outcome of surgery.

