### **11) SAFETY CONSIDERATIONS AND ADVERSE EVENTS**

Adverse events (AEs) will be recorded by investigators during any face-to-face interactions and during the fortnightly telephone reviews. These events will be documented on the CRF and reported to the CI. Participants will be requested to contact the research team via

phone or email to highlight any AEs that arise between interactions. The research team will meet to discuss AEs every 3 months, or sooner should any urgent safety measures arise.

Possible adverse events (as per separate risk assessment):

- Localised skin irritation or dermatitis
- Injury, exacerbation of underlying medical condition, slip or fall
- Inappropriate fit, catching environment/clothing
- Minor electric shock

Any new underlying pathology that is identified through this study will be highlighted to the transplant team that is primarily involved in the patients care.

Participants will be advised that they should stop exercising if they begin to feel unwell, that they let someone know and take usual medications as appropriate (such as salbutamol inhaler or GTN spray if they are already prescribed them), and to call 999 if none of the above help. This is the same as a participant would do if exerting themselves during their normal activities.

The CI is responsible for:

1. Receiving and assessing AEs and adverse reactions, noted by the research or clinical teams
2. Reporting AEs and urgent safety measures to the sponsor and REC as per the requirements of the Research Ethics Service
3. Maintaining a log of AEs occurring during the study and making this available to the sponsor on request.

Cutoff date for recording of SAEs will be at the participant 6-week post-operative follow up outpatient appointment when wearable devices will be removed and returned to the clinical team.

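### The rule removing anyone who meets an exclusion criterion after enrolment has no end date and does not separate stopping exercise from leaving follow-up, so it conflicts with Section 6.4 and may lose later outcomes in participants with serious events

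*Protocol*

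**What the plan says.** Section 6 of the protocol makes the exclusion criteria a continuing condition of participation: "Should any of the exclusion criteria take place after enrolment then the participant will be removed from the study". No period is attached, and the perioperative and recovery phases are not excepted.

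Two criteria in Section 6.2 can arise as new events after enrolment:
- the cardiovascular criterion: "Unstable angina pectoralis, recent myocardial infarction, recent cerebrovascular accident, or new arrhythmia";
- the capacity criterion: "Patient lacks capacity to give informed consent to participate in the trial".

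Section 6.4 takes a different line. On capacity it says that "any loss of capacity to consent during anaesthesia and/or whilst a patient on intensive care will be resolved at discharge", because "Participants will continue to be involved with data collection after discharge from hospital". A patient who dies during the admission "will also be included in analysis as this is an extremely important adverse outcome of surgery".

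The withdrawal list that follows Section 6.4 includes safety reasons and investigator decision but does not mention the Section 6 rule. The only consequences it gives are for participants who themselves decide to withdraw: wearable monitoring stops and standard care continues. It does not mention adverse-event or outcome follow-up.

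Section 11 sets the safety window: "Cutoff date for recording of SAEs will be at the participant 6-week post-operative follow up outpatient appointment". Section 9.11 says that post-operative complications will be listed, together with numbers screened, enrolled, withdrawn and completed.

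**The concern.** A myocardial infarction, stroke, new arrhythmia or loss of capacity is a reason not to enrol someone. After enrolment it is also something the study needs to know about, either as a possible harm of unsupervised exercise or as a post-operative complication. A rule that takes people out of the study because such an event has happened makes the completeness of follow-up depend on the outcome.

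The protocol intends to use this information. Section 4.2 asks whether transplant outcomes improve and whether wearable signals relate to outcomes. The Background promises a preliminary evaluation of post-operative outcomes to shape a larger study. If participants with serious events are followed for less time than the others, the later complications and 6-week responses passed to that study come mainly from people who did well. An analysis plan cannot recover follow-up that was never collected.

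**Working it through.** The protocol gives no figure to reproduce: Section 9.2 says no power calculation was made, and no event rate appears anywhere. The main check is a comparison of the text.

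**Step 1: does the rule reach events after surgery?** Section 6 is mandatory, applies to any exclusion criterion and is expressly about what happens after enrolment. A participant's involvement is 2 weeks of baseline, 6 weeks of exercise and 6 weeks after surgery: 2 + 6 + 6 = 14 weeks. Nothing ends the rule before week 14. An infarction or stroke within that time is recent on any ordinary reading. So the rule covers it.

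**Step 2: capacity.** Sections 6 and 6.2 together require removal when capacity is lost. Section 6.4 treats loss in anaesthesia or intensive care as temporary and continues data collection. Staff cannot follow both as written, so the conflict is direct.

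**Step 3: fatal and non-fatal events.** Section 6.4 keeps an in-hospital death in the analysis because it is an important adverse outcome. A participant who survives a post-operative stroke or infarction is to be removed. One who has a stroke and dies later in the same admission falls under both rules. The reason given for keeping deaths applies equally to serious non-fatal events, and no ground is given for treating them differently.

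**Step 4: Section 11.** Adverse events are gathered at face-to-face contacts, at the fortnightly calls and by participants' own reports. They go on the CRF, to the chief investigator and into a log. The triggering event can therefore be recorded. What is not assured is any study contact between removal and the 6-week cutoff, or the 6-week questionnaire. The tension with Section 11 is by implication only.

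**Step 5: size in the worst case.** Inputs: N = 20 (10 donors + 10 recipients, Section 9.2), up to 40 (Section 5.1). The event count is assumed. The worst case is that a removed participant leaves both numerator and denominator. Exact (Clopper-Pearson) 95% limits for x events in n are the 0.025 quantile of Beta(x, n − x + 1) and the 0.975 quantile of Beta(x + 1, n − x). With x = 0 the upper limit is 1 − 0.025^(1/n); for n = 19 this is 17.6%.

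| Enrolled | Assumed events | Everyone kept (95% CI) | Worst case after removal (upper limit) |
|---|---|---|---|
| 20 | 1 | 5.0% (0.1 to 24.9) | 0/19 (17.6%) |
| 20 | 2 | 10.0% (1.2 to 31.7) | 0/18 (18.5%) |
| 20 | 3 | 15.0% (3.2 to 37.9) | 0/17 (19.5%) |
| 40 | 1 | 2.5% (0.1 to 13.2) | 0/39 (9.0%) |
| 40 | 2 | 5.0% (0.6 to 16.9) | 0/38 (9.3%) |
| 40 | 3 | 7.5% (1.6 to 20.4) | 0/37 (9.5%) |

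**Step 6: how likely is it that the rule is triggered?** The chance of at least one event is 1 − (1 − p)^N. For assumed p of 2%, 5% and 10% it is 33%, 64% and 88% with N = 20, and 55%, 87% and 98.5% with N = 40. These rates are illustrations; the protocol gives none.

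**The case against.** The strongest reply is that removal from the study is not deletion from the data. The event comes before the removal, Section 11 has its own recording and reporting route, and Section 9.11 lists withdrawals, so a removed participant stays visible. Even someone who withdraws consent is asked whether data already collected may be used. This stands. A reader might infer that the event itself disappears and that 0/19 is what would be reported. The protocol does not say so: that result needs the event to be dropped and the denominator to shrink, and neither step is stated.

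A reader might also infer that Section 11 is flatly contradicted. It is not. It makes no exception for removed participants and does not say that recording ends at removal. The gap is that no contact is provided through which later events would be found.

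On capacity, Section 6.4 can be read as a specific exception to a general rule, and it covers the foreseeable perioperative cases. That is probably the intent. But Section 6 allows no exception, neither section refers to the other, and loss of capacity outside anaesthesia or intensive care is left uncovered.

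The rule also has a safety purpose. Section 13.21 explains that people at cardiac risk are excluded because the exercise is unsupervised. It would be wrong to conclude that the rule should be switched off once exercise begins, and this point does not ask for that.

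Finally, the study is a feasibility study, complications are only to be listed, and analysis sets may be defined in an analysis plan that is not shown. This limits the severity. It does not remove the point, because whether follow-up continues is set by the protocol.

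**Conclusion.** The point holds as an inconsistency that should be fixed. Section 6 removes participants for events that other sections want followed, sets no end date, and does not separate stopping the exercise programme from leaving follow-up. It conflicts directly with Section 6.4 on capacity lost in anaesthesia or intensive care, and does not fit that section's reason for analysing deaths. The likely consequence is missing later complications, later SAEs and 6-week questionnaires in participants who had a serious event.

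The change from 1/20 to 0/19 is an outer bound. It rests on one assumed event and on removal from both numerator and denominator. The two intervals overlap widely, and the protocol specifies no decision that depends on a complication rate. The primary feasibility question is not directly affected.

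**What to change.** Reconcile Section 6, Section 6.4 with its withdrawal list, and Section 11 on two matters: what removal means (end of the exercise programme, or end of follow-up) and the period in which the rule applies.

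Then state that a participant who meets one of these criteria after enrolment:
- has the event recorded and reported under Section 11;
- is counted in the safety and complication listings;
- stays in outcome and SAE follow-up to the 6-week visit unless consent is withdrawn.

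Whether and when exercise or device wear stops is a clinical decision for the sponsor. No change to that safety trigger is proposed here.

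The cost is a few sentences in an amendment. No visit is added, because Section 5.5 already allows the final review to take place at a scheduled outpatient appointment. The small downside is that complication counts may look less favourable.

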### 6.1 Inclusion Criteria:

- Aged 18 years and over
- Live kidney donor or transplant recipient

### 6.2 Exclusion Criteria:

[figure not shown]
- Deceased donor transplant recipient
- Patients unable to wear or tolerate the wearable device
- Unstable angina pectoralis, recent myocardial infarction, recent cerebrovascular accident, or new arrhythmia
- Patient declines or is unable to participate in the exercise programme
- Patient lacks capacity to give informed consent to participate in the trial
- Non-English language
- Patient has no access to a smart device to download the OURa/Withings Health Mate/Corsano Research Trials app

### 6.3 Recruitment:

Participants will be recruited at Manchester Royal Infirmary through the transplant team. The transplant team will identify candidates for recruitment from their outpatient work when reviewing potential donors and recipients for live kidney transplantation. At the time of identification potential participants will be provided with a participant information sheet to read about the study at a time convenient for them and complete a consent to contact form. Interested participants will then be contacted via a phone call after a minimum of 24 hours has passed. The potential participant will verbally consent to be screened for whether they would be suitable for the trial.

If a potential participant is deemed suitable for enrolment after telephone screening, they will be invited to an in-person meeting where they will be required to sign a consent form to be involved in the study. This meeting will take place in The Wearables Lab, Manchester Royal Infirmary. After completion of the consent form the participant will complete a paper-based baseline exercise and circadian rhythm questionnaire and be allocated their device. The participant will be shown the prehabilitation exercise videos and instructed as to which video(s) they should be using as part of their initial prehabilitation. Participants will also

receive a folder of paper-based post exercise surveys and a blank notebook to keep an informal patient journal.

#### 6.4 Participants who withdraw consent [or lose capacity to consent]:

Participants can withdraw consent at any time without giving any reason, as participation in the research is voluntary, without their care or legal rights being affected. There is no change to their usual management based on their participation, or withdrawal, from this study.

Participants will be asked whether any pseudonymised data collected so far, can be used as part of the analysis of the study. Data would include wearable data (biometric, activity, sleep) and paper surveys linked to their study ID only. Links between their study ID and any identifiable data would be permanently erased at the time of consent withdrawal.

Once full data collection has been completed, all data will be anonymised and no longer linked to a study ID. It would not be possible to remove individual participant data from the analysis of this trial after the point of anonymisation.

Participants will continue to be involved with data collection after discharge from hospital, therefore any loss of capacity to consent during anaesthesia and/or whilst a patient on intensive care will be resolved at discharge. For any patient that may die during their

admission, however unlikely, will also be included in analysis as this is an extremely important adverse outcome of surgery.

### **Withdrawal from study**

The reasons why participants will be withdrawn from the study are as follows:

- Participant's decision to withdraw from the study
- Investigator decision
- Safety reasons
- Severe non-compliance to protocol as judged by the investigator (participating in less than 50% of exercise sessions as monitored by their diary and wearable technology).

If a participant decides to withdraw:

- Monitoring with the wearable device will cease.
- Participants will continue with the normal standard of care.

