## **4) STUDY OBJECTIVES**

### **4.1 Primary Question/Objective:**

- Is it feasible for renal transplant patients and live kidney donors to participate in a prehabilitation programme in combination with a piece of wearable technology?

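### Failing to keep up the exercise or to tolerate the device is a ground for removal from a study that asks whether patients can do both, and nothing continues data collection for those removed

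*Protocol*

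**What the plan says.** Section 4.1 asks whether recipients and live donors can "participate in a prehabilitation programme in combination with a piece of wearable technology". Section 9.11 answers this from recruitment, compliance and the qualitative analysis of open answers, among other things. It also lists the numbers enrolled, withdrawn and completing.

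Three provisions take participants out of the study for failing at one of those two components:

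- The list headed *Withdrawal from study* in 6.4 opens with "The reasons why participants will be withdrawn from the study are as follows" and includes "Severe non-compliance to protocol as judged by the investigator (participating in less than 50% of exercise sessions". Attendance is judged from the diary and the wearable.
- Section 6 states: "Should any of the exclusion criteria take place after enrolment then the participant will be removed from the study". One criterion in 6.2 that this carries forward is "Patient declines or is unable to participate in the exercise programme".
- Another is "Patients unable to wear or tolerate the wearable device".

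The consequences of leaving are given only for other situations. Under "If a participant decides to withdraw", wearable monitoring stops and usual care goes on. For withdrawal of consent, 6.4 asks permission to use data already collected and adds: "Links between their study ID and any identifiable data would be permanently erased at the time of consent withdrawal". Nothing says what follow-up applies to a participant whom the study itself removes.

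**The concern.** In a feasibility study, low attendance, inability to exercise and device intolerance are results. Here they are also reasons for exit.

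The participants concerned are the most informative about acceptability. Section 3 makes acceptability one of four key areas and links it to finding exercise that people keep up. It also raises poor compliance as a concern for this population.

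At risk are the post-operative wearable data, the final questionnaire and the journal handed in with it (5.5). If low attendance is acted on before admission, the repeat grip test and the end-of-programme questionnaire are at risk too (5.2). The paper post-exercise surveys are also handed in at admission, and no route is given for retrieving them from someone removed earlier. These are not only secondary data: free-text answers and journals feed the thematic analysis (9.12), and open responses are a named input to the primary question (9.11). An analysis plan can define a denominator, but it cannot recover data that were never collected.

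**Working it through.** The protocol gives no figure to reproduce, so the check sets its rules against its own schedule.

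**Inputs.** At least 4 sessions a week (5.2) for 6 weeks; 2 baseline + 6 programme + 6 post-operative weeks of wear (section 5, Duration); reviews at about weeks 2 and 4 of the programme (Appendix 1); grip test and end-of-programme questionnaire at admission, final questionnaire at 6 weeks (5.2); 20 to 40 participants (5.1).

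**The threshold.** Minimum sessions = 4 × 6 = 24, and 50% of 24 = 12. The protocol does not say whether the 50% applies to sessions to date or to the whole programme, and this decides how early removal can occur:

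- Sessions to date: fewer than 4 of 8 at week 2, or fewer than 8 of 16 at week 4, could trigger it.
- Whole programme: at week 2, done + 16 < 12 is impossible, so nobody is certain to miss it. At week 4, done + 8 < 12 requires 3 or fewer of 16.

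**Loss per removed low attender, if removal ends collection.** Planned wear = 2 + 6 + 6 = 14 weeks, inpatient days not counted.

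| Removal acted on | Wear weeks lost | Pre-operative weeks lost (of 8) | Later assessments lost |
|---|---|---|---|
| Week-2 call | 4 + 6 = 10 of 14 (71%) | 4 (50%) | 3 of 3 |
| Week-4 call | 2 + 6 = 8 of 14 (57%) | 2 (25%) | 3 of 3 |
| Admission, after that day's assessments | 6 of 14 (43%) | 0 | 1 of 3 |

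The wear-week columns do not apply to someone removed because the device cannot be worn; that person would not supply those weeks under any rule. The loss of assessments and of the journal does apply.

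**Number affected.** This is not given. Assuming 1, 2, 4 or 6 removals: 5%, 10%, 20% or 30% of 20 participants, or 2.5%, 5%, 10% or 15% of 40.

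**Compliance summary (conditional).** If all enrolled are counted, there is no overstatement. If only retained participants were summarised, the share attending at least half the sessions would read about 100% whatever the truth. With 4 of 20 removed for low attendance, the all-enrolled figure would be 16/20 = 80%. The protocol does not say that removed participants leave the summary.

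**The case against.** The strongest reply is that the loss is inferred. The only stated research consequence of leaving is the end of device monitoring, and that is written for a participant who chooses to go. Nothing expressly cancels questionnaires or journal return. Likewise, nothing says that record extraction (8.3) or adverse event recording (section 11) stops, and no loss of either is claimed. The inference is nevertheless the ordinary meaning of being withdrawn or removed from a study. If the sponsor intends otherwise, the protocol has to say so.

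Second, the feasibility signal is partly kept: withdrawals are counted, and the attendance that triggers removal has already been observed. This stands, and it is why overstated compliance is only a conditional risk. But a count does not explain why people failed, and it recovers no later data.

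Third, the 71% figure assumes early action and mixes objectives. Written exercise records come in at admission or later, so admission is a natural decision point, and the six post-operative weeks chiefly serve the secondary questions. These points are fair, and the table shows the smaller figures. Cloud data and the fortnightly calls still permit earlier action, and even removal at admission loses the final questionnaire and the scheduled journal return.

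Fourth, the 50% rule leaves room for the investigator's judgement. It does, but the section 6 rule does not.

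Fifth, the population for the compliance summary could be set in an analysis plan. That is correct, and the finding does not depend on it.

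**Conclusion.** The concern holds and should be fixed. The removal rules conflict with the primary objective: failing at either component of the feasibility question is a reason to leave the study, and no provision continues data collection afterwards.

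For a removed low attender, the loss runs from 6 of 14 wear weeks and 1 of 3 later assessments to 10 of 14 and all 3, depending on when removal is acted on. For a participant who cannot tolerate the device, it is the questionnaires, journal and grip test that matter.

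This rests on two things the protocol leaves open: that removal ends collection, and how many participants are removed. Confidence is therefore medium. With a target of 20, each removed participant is 5% of the sample and among those with most to say about acceptability.

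**What to change.** In section 6 and in the withdrawal list of 6.4, separate stopping the programme or the device from leaving the study. State that low attendance, later declining or being unable to exercise, or not tolerating the device does not by itself end data collection. With continued consent, keep these participants for the admission and 6-week assessments, the questionnaires, journal return and, where tolerated, wearable monitoring. Say whether any 50% attendance figure refers to sessions to date or to the whole programme. Confirm that adverse event recording continues to the 6-week cutoff.

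In 9.11, or in the analysis plan, add that compliance is summarised over all enrolled participants, counting early stoppers at the sessions they completed. None of this takes a position on when anyone should stop exercising, and the other exclusion criteria stay as they are.

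The cost is a text amendment in two places and one sentence on analysis, with no extra participants, visits or calls. Reported compliance may look less favourable. Each device kept in use stays out about 6 to 10 weeks longer than under removal, and device supply partly limits the sample (9.2). If supply binds, the device can be taken back while the visits and questionnaires continue, which still saves the questionnaires, journal and grip test.
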